11.2 Monitoring for Adverse Events

At each visit, after the subject has had the opportunity to spontaneously mention any problems, the Investigator should inquire about AEs by asking the standard questions shown below and report as applicable:

- "Have you had any health problems since your last study visit?"
- "Have there been any changes in the medicines you take since your last study visit?"

In addition, changes in *any protocol-specific parameters* evaluated during the study are to be reviewed by the Investigator. Any untoward (unfavorable and unintended) change in *a protocol-specific parameter* that is clinically relevant, in the opinion of the Investigator, is to be reported as an AE. These clinically relevant changes will be reported regardless of causality.

11.3 Procedures for Recording and Reporting

AEs are collected from the time of informed consent. Any pre-existing medical conditions or signs/symptoms present in a subject prior to the start of the study (ie, before informed consent is signed) are not considered AEs in the study and should be recorded in the Medical History section of the eCRF.

In addition, dry eye, superficial punctate keratitis, and optical visual disturbances (eg, glare, halo, and starburst) are examples of early post-operative findings that are typically observed following kerato-refractive surgery. These are not considered AEs if they can be reasonably expected to resolve within 6 months and not result in any untoward long term visual outcome impact. However, based on the Investigator's medical judgment, signs and symptoms of dry eye and ocular visual disturbances prior to 6 months, or persisting beyond 6 months post kerato-refractive surgery, may be considered an AE.

For each recorded event, the ADEs and SAEs documentation must include: date of occurrence, severity, treatment (if applicable), outcome, and assessments of the seriousness and causality. In addition, the Investigator must document all device deficiencies reported or observed with test and control products on the Device Deficiency eCRF. The site must submit all available information on ADEs, SAEs, and device deficiencies to the Study Sponsor immediately as follows:

• ADEs or SAEs are documented on the *Serious Adverse Event and Adverse Device Effect* eCRF within 24 hours of the Investigator's or site's awareness.

- Device deficiencies are documented on the *Device Deficiency* eCRF within 24 hours of the Investigator's or site's awareness.
- A printed copy of the completed *Serious Adverse Event and Adverse Device Effect* and/or *Device Deficiency* eCRF must be included with product returns.
- Additional relevant information after initial reporting must be entered into the eCRF as soon as the data become available.
- Document any changes to concomitant medications on the appropriate eCRFs.
- Document all relevant information from Discharge Summary, Autopsy Report,
 Certificate of Death, etc, if applicable, in narrative section of the Serious Adverse
 Event and Adverse Device Effect eCRF.

Note: Should the EDC system become non-operational, the site must complete the appropriate paper Serious Adverse Event and Adverse Device Effect and/or Device Deficiency Form. The completed form is emailed to the Study Sponsor at [contact] according to the timelines outlined above; however, the reported information must be entered into the EDC system once it becomes operational.

Any AEs and device deficiencies for non-study marketed devices/products (eg, FS200, Custom Paks, etc.) will be considered and processed as spontaneous (following the post-market vigilance procedures) and should be communicated to the device's/product's manufacturer as per local requirements.

Study Sponsor representatives may be contacted for any protocol related question and their contact information is provided in the Manual of Procedures that accompanies this protocol.

Further, depending upon the nature of the AE or device deficiency being reported, the Study Sponsor may request copies of applicable portions of the subject's medical records. The Investigator must also report all AEs and device deficiencies that could have led to a SADE according to the requirements of regulatory authorities or IRB/IEC.

Intensity and Causality Assessments

Where appropriate, the Investigator must assess the intensity (severity) of the AE based on medical judgment with consideration of any subjective symptom(s), as defined below:

Intensity (Severity)

Mild An AE is mild if the subject is aware of but can easily tolerate the sign or

symptom.

Moderate An AE is moderate if the sign or symptom results in discomfort significant

enough to cause interference with the subject's usual activities.

Severe An AE is severe if the sign or symptom is incapacitating and results in the

subject's inability to work or engage in their usual activities.

For every AE in the study, the Investigator must assess the causality (Related or Not Related to the medical device or study procedure). An assessment of causality will also be performed by Study Sponsor utilizing the same definitions, as shown below:

Causality

Related An AE classified as related may be either definitely related or possibly related

where a direct cause and effect relationship with the medical device or study procedure has not been demonstrated, but there is a reasonable possibility that

the AE was caused by the medical device or study procedure.

Not Related An AE classified as not related may either be definitely unrelated or simply

unlikely to be related (ie, there are other more likely causes for the AE).

The Study Sponsor will assess the AEs and may upgrade the Investigator's assessment of seriousness and/or causality. The Study Sponsor will notify the Investigator of any AEs that is upgraded from non-serious to serious or from unrelated to related.

Furthermore, the Study Sponsor shall promptly conduct an evaluation of any unanticipated adverse device effect, including anticipated adverse events that occur in unanticipated severity or frequency. The results of this evaluation will be reported to the FDA, the IRB, and participating Investigators within 10 working days upon receiving notification of the effect.

11.4 Return Product Analysis

Study Sponsor representatives and their contact information are provided in the MOP that accompanies this protocol.

Alcon products associated with device deficiencies and/or product related AEs should be returned and must include the Complaint # which will be provided by Study Sponsor after the case is entered in the Study Sponsor's Global Product Complaint Management System.

11.5 Unmasking of the Study Treatment

Not applicable; this study is open-label.

11.6 Follow-Up of Subjects with Adverse Events

The Investigator is responsible for adequate and safe medical care of subjects during the study and for ensuring that appropriate medical care and relevant follow-up procedures are maintained after the study.

The Investigator should provide the Study Sponsor with any new safety information (which includes new AEs and changes to previously reported AEs) that may affect the safety evaluation of the device. For AEs that are unresolved/ongoing at time of subject exit from study, any additional information received at follow-up should be documented in the eCRFs up to study completion (ie, database lock).

Any additional data received up to 6 months after subject discontinuation or exit must be documented and available upon the Study Sponsor's request. All complaints received after this time period will be considered and processed as spontaneous (following the post-market vigilance procedures) and should be communicated to the medical device's manufacturer as per local requirements.

The Investigator should also report complaints on non-Alcon products directly to the manufacturer as per the manufacturer's instructions or local regulatory requirements.

11.7 Pregnancy in the Clinical Study

Pregnancy is not reportable as an AE; however, complications may be reportable and will be decided on a case—by-case basis. An Alcon form will be utilized to capture all pregnancy-related information until birth of the child.

12 ANALYSIS PLAN

This information will also be contained within a separate biostatistical analysis plan which will be prepared and finalized prior to database lock.

Counts and percentages will be presented as categorical variables. N, mean, standard deviation, median, minimum, and maximum will be presented for continuous variables.

12.1 Subject Evaluability

Final subject evaluability must be determined prior to locking the database, based upon the Deviations and Evaluability Plan.

12.2 Analysis Sets

All eligible subjects will be screened to determine if they meet all inclusion and no exclusion criteria. Subjects who provide informed consent will be considered enrolled in the study.

12.2.1 Safety Analysis Set

The safety analysis set (SAF) will contain all eyes that undergo surgery or attempted surgery (defined as eye drops given for flap treatment); the SAF will be the primary analysis set for the safety analyses.

12.2.2 Full Analysis Set

The full analysis set (FAS) will contain all eyes that successfully undergo surgery; the FAS will be the primary analysis set for the effectiveness analyses.

12.2.3 Consistent Cohort Analysis Set

The consistent cohort (CC) will contain all eyes in the FAS that have manifest refraction data at all post-operative visits from one month up to and including the visit where refractive stability is established. The CC will be the primary analysis set for the refractive stability analyses.

12.3 Demographic and Baseline Characteristics

Demographic and baseline characteristics will be summarized for each subject. Appropriate summary statistics will be presented for each characteristic. These summaries will be based on the FAS.

12.4 Refractive Stability

Stability analyses will be performed on eyes that have every follow-up exam from 1-month up to the stability time point (the CC), as well as on the eyes that have 2 consecutive exams, but not necessarily every follow-up exam. The following stability analyses will be performed for the time intervals between all consecutive pairs of scheduled postoperative refractions:

• Percentage of eyes that achieve:

- o a change of less than or equal to 1.00 D of MRSE between two refractions performed at 1 month and 3 months, and between subsequent refractions performed at least 3 months apart;
- o a change of less than or equal to 0.50 D of MRSE between two refractions performed at 1 month and 3 months, and between subsequent refractions performed at least 3 months apart;
- Mean overall change and change per month in MRSE between consecutive scheduled visits as determined by a paired analysis;
- Mean \pm SD MRSE for the preoperative and each postoperative visit;
- Assessment of cylinder stability for correction of spherocylindrical refractive errors

Refractive stability is achieved at the latter of two postoperative manifest refractions performed at least 3 months apart or at 3 months after surgery when compared with the 1-month interval, when all of the following recommended criteria are met:

- At least 95% of the treated eyes have a change ≤ 1.00 D of MRSE between the 2 refractions;
- The mean rate of change in MRSE, as determined by a paired analysis, is ≤ 0.5 D per year (0.04 D/month) over the same time period;
- The mean rate of change of MRSE decreases monotonically over time, with a projected asymptote of zero or a rate of change attributable to normal aging;
- The 95% confidence interval for the mean rate of change in MRSE includes zero or a rate of change attributable to normal aging; and
- Stability is confirmed at least 3 months after the stability time point by a statistically adequate subgroup (at least 80% of the cohort).

The primary safety and effectiveness endpoints for the study can only be evaluated once refractive stability has been established within the CC, as well as on the eyes that had 2 consecutive exams, but not necessarily every follow-up exam.

12.5 Effectiveness Analyses

12.5.1 Analysis of Primary Effectiveness Endpoints

In order to establish effectiveness of the WaveLight EX500 excimer laser system for the correction of myopia with and without astigmatism using InnovEyes in conjunction with InnovEyes sightmap, the following four co-primary endpoints are defined:

- Percentage of eyes with UCDVA of 20/40 (in eyes with preoperative BCDVA of 20/20 or better) or better at refractive stability (Target: ≥ 85%)
- Percentage of eyes with MRSE within 0.50 D at refractive stability (Target: $\geq 50\%$)
- Percentage of eyes with MRSE within 1.00 D at refractive stability (Target: $\geq 75\%$)
- Percentage of eyes that achieve refractive stability (Target: $\geq 95\%$)

[figure not shown]
12.5.1.1 Statistical Hypotheses

No hypothesis testing of the primary effectiveness endpoints is planned.

12.5.1.2 Analysis Methods

The FAS will be used for this analysis. The number and percentage of eyes meeting each of the primary effectiveness endpoints will be calculated. The effectiveness criteria will be considered to have been met if the percentage meets or exceeds the target rate at the time of refractive stability for all primary effectiveness endpoints. These analyses will be performed for the whole FAS

An analysis will be performed once refractive stability is achieved; a final summary of these endpoints will be performed once the one year follow-up is complete.

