5 EFFECTIVENESS ANALYSIS STRATEGY

For analysis of refractive outcomes, the spherical component of the manifest and cycloplegic refractions (as tested at 4.0 m) will be adjusted for optical infinity by adding -0.25 D to the spherical magnitude for all post-operative assessments. Similarly, manifest refraction

spherical equivalent (MRSE) will be calculated using the respective adjusted manifest and cycloplegic sphere values.

Unless otherwise specified, MRSE will be based on the subject's manifest refraction, not on the value collected by the sightmap device (measured refraction). Additionally, all visual acuity categories will be determined using logMAR values.

For analyses involving visual acuity, Snellen lines will be based on the conversion from logMAR line ± 2 letters (e.g., 20/20 Snellen = -0.04 to 0.04 logMAR).

Note: Effectiveness analyses based on FAS or CC excludes all data/subjects that have met any of the Data Set Analysis Restrictions (DSARs) identified in the Deviation and Evaluability Plan (DEP).

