5.1.2 Analysis Methods

[figure not shown]
The FAS will be used for this analysis. The number and percentage of eyes meeting each of the primary effectiveness endpoints will be calculated. The effectiveness criteria will be considered to have been met if the percentage meets or exceeds the target rate at the time of refractive stability for all primary effectiveness endpoints. These analyses will be performed for the whole FAS

An analysis will be performed once refractive stability is achieved; a final summary of these endpoints will be performed once the one year follow up is complete.

Document ID: Status: Approved, Version: 4.0 V-CLN-0000922 Approved Date: 30 Nov 2022

[figure not shown]

[figure not shown]

[figure not shown]

[figure not shown]

[figure not shown]
Document ID:

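### Does the choice between the FAS and the consistent cohort leave co-primary endpoint 4 (at least 95% of eyes stable) without a usable denominator?

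*Protocol*

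**What the plan says.** Protocol 12.5.1 and SAP 5.1 list four effectiveness co-primaries. The fourth is "Percentage of eyes that achieve refractive stability", with a 95% target, and effectiveness requires all four targets to be met.

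Three statements bear on who is counted:

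- **FAS.** Protocol 12.2.2: "The full analysis set (FAS) will contain all eyes that successfully undergo surgery". For the effectiveness co-primaries SAP 5.1.2 says: "The FAS will be used for this analysis". Both documents then add: "These analyses will be performed for the whole FAS".
- **CC.** Protocol 12.2.3: "The CC will be the primary analysis set for the refractive stability analyses". Membership needs a manifest refraction at every visit from one month to the stability visit.
- **Stability rule.** Protocol 12.4 and SAP 4 run the stability analyses on the CC and also on eyes with two consecutive exams. The first criterion reads: "At least 95% of the treated eyes have a change ≤ 1.00 D of MRSE between the 2 refractions". The remaining criteria describe the cohort: mean rate of change, its confidence interval, its trend over time, and confirmation in at least 80%.

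Two more statements qualify these. Protocol 12.6 plans no imputation. SAP 5 notes: "Effectiveness analyses based on FAS or CC excludes all data/subjects that have met any of the Data Set Analysis Restrictions". Those restrictions are in a separate plan that is not part of the documents.

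**The concern.** Endpoint 4 is at once a primary effectiveness endpoint, which points to the FAS, and a stability result, which points to the CC. FAS membership depends only on successful surgery, whereas CC membership requires complete refractions. The visible text neither says when a single eye counts as stable nor what happens to an FAS eye with a missing refraction.

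Taken literally, the reference to the whole FAS suggests that every operated eye belongs in the denominator. Endpoint 4 is the only effectiveness co-primary whose target (95%) exceeds the retention implied by the plan's own loss allowance in Protocol 8 (up to 10%, so 90%). Missing eyes alone could then fail the trial on effectiveness, however well the examined eyes did. The study is also unmasked, so an unwritten denominator could in principle be chosen with the data in view.

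**Working it through.** **Inputs.** 374 eyes treated (Protocol 12.9); loss of up to 10%, with no time point (Protocol 8); target 95% (Protocol 12.5.1). The plan computes no figure for this endpoint. Its one calculation, the chance of seeing a 1% event, is not an input here.

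**Eye-level definition (an inference).** An eye is taken as stable if its MRSE changes by at most 1.00 D over the interval ending at the stability visit. Of the criteria for declaring stability, only the first can be scored on one eye, and it carries the same 95%.

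**Reading A: missing eyes kept in the denominator and counted as not stable.**

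- Eyes needed: 0.95 × 374 = 355.3, so 356.
- Missing eyes allowed: 374 − 356 = 18, and 18/374 = 4.8%.
- At 10% loss: 37 missing, 337 seen, ceiling 337/374 = 90.1%.

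**Reading B: eyes with both refractions only.**

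- At 337 seen: 0.95 × 337 = 320.15, so 321 stable eyes are enough (321/337 = 95.3%).

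| Missing | Stable / seen | Reading B | Reading A (÷ 374) |
|---|---|---|---|
| 11 | 359/363 | 98.9%, met | 96.0%, met |
| 11 | 352/363 | 97.0%, met | 94.1%, not met |
| 19 | 355/355 | 100%, met | 94.9%, not met |
| 37 | 337/337 | 100%, met | 90.1%, not met |
| 37 | 327/337 | 97.0%, met | 87.4%, not met |
| 37 | 317/337 | 94.1%, not met | 84.8%, not met |

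**Does FAS versus CC cause the split?** No. Protocol 12.4 states: "The primary safety and effectiveness endpoints for the study can only be evaluated once refractive stability has been established within the CC", and extends this to the eyes with two consecutive exams. Under the inferred definition, criterion 1 has then already shown at least 95% stable in the CC and in the observed pairs. FAS eyes with both refractions of the interval are those observed pairs, so endpoint 4 is met on either set. The last table row would not reach evaluation. The verdicts part only if missing eyes are scored as failures.

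**Does the plan support that scoring?** Four features of the text point the other way.

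1. Counting an unobserved eye as not stable assigns it an outcome, which fits poorly with Protocol 12.6.
2. Criterion 1 speaks of treated eyes, yet the plan applies it to the CC and to eyes with two consecutive exams. Eyes without refractions lie outside both. In the plan's own usage, a 95% share of treated eyes is a share of examined eyes.
3. The FAS is not literally every operated eye in the effectiveness analyses. SAP 5 removes restricted data, and Protocol 8.2 excludes data from subjects who become pregnant.
4. The sentence about the whole FAS has no full stop in either document and appears cut off. SAP 6.1.2 goes on to summaries by site, race and ethnicity, age and gender for the safety endpoints. A parallel contrast with subgroups is a plausible sense of the word whole here.

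The overlap of sets also resolves by position. The stability analyses are those of Protocol 12.4 and SAP 4, where the CC is primary. Endpoint 4 is listed under effectiveness, where the FAS is named specifically.

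**The case for a change.** The strongest case for a change is that the documents do say whole FAS, define that set by surgery alone, and never state a denominator. Whether counting an unseen eye as not having achieved stability is imputation can be argued. The limit under Reading A is tight: ten of 187 subjects without a needed refraction means 20 eyes, and 354/374 = 94.7% already falls short. Missed visits count as well as losses. If visits are missed independently at rate m, solving (1 − m)² = 356/374 gives m = 2.4% at each of two visits. One sentence would remove the doubt at little cost.

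The arithmetic stands, and so does the observation that no eye-level definition or explicit denominator is visible. What does not stand is that the plan leaves two equally good readings. The 10% is an upper figure without a time point, and stability can be declared as early as three months, when loss may be lower. The sentence one would add records what an analyst following Protocol 12.4 and 12.6 would do anyway. The endpoint so written would repeat criterion 1 on the same eyes, so the amendment would bring no new evidence.

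**Conclusion.** No change is needed. This is a gap that analysts fill sensibly: endpoint 4 is computed on FAS eyes with both refractions of the stability interval, and the CC serves the Protocol 12.4 and SAP 4 analyses. Under that reading FAS and CC agree, and the endpoint is met whenever the precondition for evaluating it is met.

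The opposite result needs missing eyes counted as not stable and more than 18 of 374 eyes missing, or fewer missing combined with some observed instability. The ceilings (4.8% missing allowed; 90.1% at 10% loss) are exact for 374 eyes. The agreement between sets rests on taking a change of at most 1.00 D as the eye-level definition, and on criterion 1 being computed on eyes with data, as the plan describes.

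Attrition would not be hidden, because SAP 3 provides a subject disposition table. The Deviation and Evaluability Plan and the withheld SAP text could not be checked and may already state the rule.

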12.6 Handling of Missing Data

No imputation of missing data is planned.

12.7 Safety Analyses

All adverse events occurring from the time a subject signs informed consent to study exit will be accounted for in the reporting. Safety analyses will be conducted using the SAF through descriptive summaries (counts and percentages) and listings. In addition, separate subject listings will be provided for AEs that occur in subjects:

- after signing informed consent but prior to exposure to IP (InnovEyes sightmap)
- exposed to IP (InnovEyes sightmap) but do not proceed to InnovEyes treatment (and thus are not included in the SAF)

12.7.1 Analysis of Primary Safety Endpoints

In order to establish safety of the WaveLight EX500 excimer laser system for the correction of myopia with and without astigmatism using InnovEyes in conjunction with InnovEyes sightmap, the following four co-primary endpoints are defined:

[figure not shown]
- Percentage of eyes that lose 2 lines or more of BCDVA (Target at refractive stability ≤ 5%)
- Percentage of eyes with BCDVA worse than 20/40 (for eyes with BCDVA of 20/20 or better pre-op) (Target at refractive stability ≤ 1%)
- Percentage of eyes that have an increase of manifest refractive astigmatism of greater than 2.00 D of absolute cylinder as compared to the preoperative refraction (Target at refractive stability ≤ 5%)
- Percentage of eyes with a serious, non-flap related, ocular adverse event at the postoperative visits (Target per event type at refractive stability: ≤ 1%)

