11 ADVERSE EVENTS AND DEVICE DEFICIENCIES

11.1 General Information

An AE is any untoward medical occurrence, unintended disease or injury, or untoward clinical signs (including abnormal laboratory findings) in subjects, users, or other persons, whether or not related to the investigational medical device (test product). Refer to the Glossary of Terms and figures below for categories of AEs and SAEs.

Figure 11–1 Categorization of All Adverse Events

[figure not shown]
[figure not shown]

Figure 11–2 Categorization of All Serious Adverse Events

Specific Events Relevant to this Protocol

In addition to reporting all AEs (serious and non-serious) meeting the definitions, the Investigator must report any occurrence of the following as an ocular SAE:

- Diffuse lamellar keratitis (Grade 3 or above)
- Corneal infiltrate or ulcer
- Any persistent corneal epithelial defect at one month or later
- Corneal edema at 1 month or later (specify flap or bed)
- Epithelium in the interface with loss of 2 lines (10 letters) or more BCDVA

- Miscreated flap (lost, incomplete, too thin)
- Melting of the flap
- IOP with increase of > 10 mmHg above baseline on two consecutive examinations or an IOP greater than 30 mmHg on two consecutive examinations
- Haze beyond 6 months with loss of 2 lines or greater (≥ 10 letters ETDRS) of BCDVA
- Decrease in BCDVA of greater than or equal to 2 lines (≥ 10 letters ETDRS) not due to irregular astigmatism as shown by rigid contact lens refraction at 3 months or later
- Retinal detachment
- Retinal vascular accidents
- Ocular penetration
- Any other vision-threatening event

The Investigator must also report the following ocular AEs:

- Diffuse lamellar keratitis (Grade 2 or less)
- Corneal edema between one week and 1 month after the procedure
- Peripheral corneal epithelial defect at 1 month or later (location of the defect to be identified as on, off, or across the flap)
- Epithelium in the interface
- Foreign body sensation at 1 month or later
- Pain at 1 month or later
- Ghost/double images in the operative eye
- Flap is not of the size and shape as initially intended or microkeratome stopped in midcut or resultant flap is misaligned

AEs that occur in association with a device that is used in conjunction with the FS200 laser system will be reported separately from those occurring with the EX500 laser or sightmap.

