This list is consistent with the categories provided in ANSI Z80.11 2012(R2017). Any other potentially sight-threatening event may also be considered serious based on the judgment of the Investigator and should be reported appropriately as delineated in Section 11.3.

Device Deficiencies

A device deficiency may or may not be associated with subject harm (ie, ADE or SADE); however, not all ADEs or SADEs are due to a device deficiency. The Investigator should determine the applicable category for the identified or suspect device deficiency and report any patient harm separately. Examples of device deficiencies include the following:

- Calibration issue: Error in or Unable to calibrate laser or diagnostic device
- Computer software issue or system error message
- Defective component
- Detachment of device or device component
- Device breakage (eg, headrest, chin rest, and joystick)
- Device emits odor (eg, gas leak, and smoke)
- Failure of laser firing
- Failure to meet product specifications (eg, incorrect laser assembly)
- Failure to transmit record
- Foreign material present in device
- Image display error
- Incorrect laser output energy
- Incorrect measurement
- Instructions difficult to understand/follow
- Lack of effectiveness
- Mechanical issues (e.g., failure to focus, align, track, position, or unintended system motion)
- No display or display failure
- Poor quality image
- Power issue: Equipment will not power on; power loss; or intermittent connection
- Suspect product contamination (patient interface)
- Unable to capture image
- Other events that may meet the definition of device deficiency

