12.7.1.2 Analysis Methods

The SAF will be used for this analysis. The number and percentage of eyes experiencing each of the primary safety endpoints will also be calculated. The safety criteria will be considered to have been met if the percentage is less than the target rate at the time of refractive stability for all of the primary safety endpoints.

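### Do the 5% limit on acuity loss and the 1% limit on each type of serious ocular event contradict each other?

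*Protocol*

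**What the plan says.** Protocol 12.7.1 and SAP 6.1 define four co-primary safety endpoints. Two matter here.

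- The acuity-loss endpoint: "Percentage of eyes that lose 2 lines or more of BCDVA (Target at refractive stability ≤ 5" per cent.
- The serious-event endpoint: "Percentage of eyes with a serious, non-flap related, ocular adverse event at the postoperative visits (Target per event type at refractive stability", with a target of at most 1%. SAP 6.1.2 confirms that the 1% applies to each event type separately, not to all types together.

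The safety criteria are met "if the percentage is less than the target rate at the time of refractive stability for all of the primary safety endpoints" (Protocol 12.7.1.2), so failing either limit fails the safety assessment. No hypothesis test is planned; observed percentages are compared with targets.

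The link between the two is Protocol 11.1. It says "the Investigator must report any occurrence of the following as an ocular SAE", and the list that follows includes "Decrease in BCDVA of greater than or equal to 2 lines (≥ 10 letters ETDRS) not due to irregular astigmatism", a cause to be judged "as shown by rigid contact lens refraction at 3 months or later". The section adds: "This list is consistent with the categories provided in ANSI Z80.11 2012(R2017".

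Protocol 12.4 sets the earliest possible stability time point: "or at 3 months after surgery when compared with the 1-month interval".

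**The concern.** Read together, these sections seem to judge one outcome against two limits. Stability cannot be declared before the 3-month visit, so the timing condition of the listed event is already met at whichever visit is the stability visit. An eye that has lost 10 or more letters there, for a reason other than irregular astigmatism or the flap, counts under both endpoints. Because all endpoints must be met, the 1% limit could decide the verdict and the stated 5% might never come into play.

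The stakes would be real. The study is open label, the sponsor may file for approval on the stability analysis (Protocol 7.1), and the verdict could turn on the cause recorded for a handful of eyes.

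**Working it through.** **Inputs.** Up to 374 treated eyes (Protocol 12.9). Up to 10% loss to follow-up and at least 300 eyes followed (Protocol 8). Limits of 5% and 1%, with a less-than decision rule (Protocol 12.7.1.2). Lines counted as a logMAR line plus or minus 2 letters (SAP 6), at 0.02 logMAR per letter. Entry BCDVA of 0.04 logMAR or better (Protocol 8.1).

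**The plan's own figure.** The sample size statement gives about 95% probability of seeing an event type with 1% incidence. 1 − 0.99^374 = 97.7% and 1 − 0.99^300 = 95.1%, so the figure fits the 300 eyes expected to be followed. It does not bear on how the two limits relate.

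**Which eyes count under both.** Going through every starting letter within the SAP's bands, a loss of 6 to 9 letters is 1 or 2 lines, exactly 10 letters is always 2 lines, and more than 10 is 2 or more. At the stability visit the listed event therefore lies wholly inside the acuity-loss endpoint. The reverse is not true. Three kinds of loss fall under the 5% limit only:

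- losses shown to be due to irregular astigmatism;
- losses of 6 to 9 letters that cross two bands, such as 0.04 to 0.16 logMAR (0.12 / 0.02 = 6 letters);
- flap-related events.

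The limits are nested, not identical.

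**Largest passing counts**

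| Eyes | Under 5% | Under 1% | Opposite verdicts if all losses are the listed event |
|---|---|---|---|
| 374 | 18 (4.81%) | 3 (0.80%) | 4 to 18 |
| 337 (374 less 10%) | 16 (4.75%) | 3 (0.89%) | 4 to 16 |
| 300 | 14 (4.67%) | 2 (0.67%) | 3 to 14 |

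For the full 18 losses at 374 eyes to pass both limits, 15 of them (15/18 = 83%) must fall outside the listed event.

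**How often this would matter.** The documents give neither a loss rate nor the share of losses meeting the definition, so both are assumed. With independent eyes and n = 374, P(pass 5%) = P(X ≤ 18) and P(pass 1%) = P(Y ≤ 3), with X and Y binomial and Y's rate equal to the loss rate times the share.

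| Loss rate | Pass 5% | Pass 1%, all qualify | Half qualify | A tenth qualify |
|---|---|---|---|---|
| 1% | >99.9% | 48.5% | 88.0% | 99.9% |
| 2% | >99.9% | 5.8% | 48.5% | 99.3% |
| 3% | 98.1% | 0.4% | 18.7% | 97.3% |

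If both eyes of a subject always share the outcome (187 subjects, at most 9 and 1 passing), a 2% loss rate gives 99.5% for the 5% limit, and 11.0% (all qualify) or 44.1% (half) for the 1% limit. The result depends almost entirely on the assumed share.

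**The plan's own pattern.** A third safety endpoint limits BCDVA worse than 20/40 to 1%. With the SAP's bands, that means worse than 0.34 logMAR, so 0.36 or more. From entry at 0.04 or better, the loss is at least (0.36 − 0.04) / 0.02 = 16 letters. Every such eye is also a 2-line loss, so a 1% limit already sits inside the 5% limit by design. The effectiveness endpoints nest as well: spherical equivalent within 0.50 D (at least 50%) lies inside within 1.00 D (at least 75%).

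**Visits.** The serious-event endpoint mentions the postoperative visits, but its target and the decision rule are both tied to refractive stability. Stability must be confirmed at least 3 months later, and the 12-month visit is the last, so that visit cannot be the stability visit. At most the 3-, 6- and 9-month visits count up to stability. At an assumed 0.5% loss per visit, the 1% limit passes with 88% if one visit counts or if losses persist. If losses in the same eye were independent across those three visits, the rate would be 1 − 0.995^3 = 1.49% and the limit would pass with 19%. Nothing in the documents supports that independence, so 19% is an extreme.

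**The case for a change.** The strongest case for a change rests on the rigid contact lens refraction. It decides whether a loss is held to 1% or only to 5%, yet it appears in neither the schedule of assessments nor the procedure descriptions. Neither public document says how an eye without that test is classed. With unmasked sites and sponsor, a rule settled only when the data are in view could decide the verdict.

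Part of this stands: the public text does not give the classing rule, nor the exact visits that count for the serious-event endpoint. But Protocol 10.2 refers procedural detail to the Manual of Procedures, SAP 6.1.2 says flap relation is marked on the adverse event form, and the SAP text between 6.1.2 and 6.3 is not public. Any of these may hold the answer, so the gap cannot be counted as missing from the plan. The cause is also tied to a test rather than left to opinion, and Protocol 11.3 provides for the sponsor to upgrade seriousness or causality; it mentions no downgrading. An analyst facing an eye without the test can count it as the listed event, which is the stricter choice, and report it as such.

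The proposed remedies add little. Stating that both limits apply leaves every count and verdict as it is. Judging BCDVA loss by the 5% limit alone would drop a published safety comparison in an open-label study; that loosens a criterion without correcting an error. Both percentages are in any case part of the planned output, since SAP 6.1.2 reports the count and percentage for each primary safety endpoint and makes the 1% comparison by event type.

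**Conclusion.** The overlap is real, but it is not a defect. On the visible text, a loss of 10 or more letters at the stability visit that meets the Protocol 11.1 definition counts under both endpoints, and the 1% limit can fail the study while the 5% limit is met: 4 to 18 qualifying eyes at 374, 4 to 16 at 337, 3 to 14 at 300. Those ranges assume that every 2-line loss is the listed event and that the listed item is one event type.

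A broad limit with a tighter one on a defined subset is coherent, and the plan uses the same structure for acuity worse than 20/40. The 5% limit keeps its own role for losses due to irregular astigmatism, flap-related losses and 6-to-9-letter losses. The pass probabilities illustrate sensitivity to assumed rates and shares, and are not forecasts. The remaining open details are ones an analyst can fill sensibly or that may already be set outside the public text. No change to the plan follows.
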